| Rationale and background : | 
COPD is a debilitating disease characterized by poorly reversible airflow limitation, breathlessness on exertion (1-2), exercise intolerance (3) and limitations in the capacity to perform daily activities (4-5).
 
In studies that have explored patient perspectives regarding the burden and impact of COPD, predominant complaints are shortness of breath and limitations in the ability to participate in activities (6), which negatively impact on social interactions and result in loss of independence (7-8).
 
Patient satisfaction with their medication is shown to affect treatment-related behaviors, such as their likelihood of continuing to use their medication, to use their medication correctly and to adhere with medication regimen (9). Treatment satisfaction may give useful insights not only into the patients' perspective on their current treatment but also about differentiation among alternative treatments. Treatment satisfaction is defined as the individual's rating of important attributes of the process and outcomes of his/her treatment experience (11). It focuses on one aspect of satisfaction with medical care and involves the interaction of expectations, preferences, and satisfaction with medical treatment. Treatment satisfaction assessment is potentially useful for understanding the patient's perspective on their current treatment and can be helpful to differentiate among alternative treatments (14-15). Patient expectations, demographic characteristics, such as age and education, and personal preferences affect treatment satisfaction. The pattern and characteristics (that is, side effects and effectiveness) of ongoing treatments for COPD, and the duration/severity of COPD influence perceptions of treatment satisfaction. More important are the factors most directly connected to the treatment, and the way the treatment is delivered and directly experienced by the patient. Outcomes of treatment, including impact on symptoms and adherence with the treatment regimen, represent an important determinant of treatment satisfaction. In 2012 only the 14.3% of Italian patients affected by obstructive respiratory syndromes was adherent to treatment (48)
 
The complexity, discomfort and convenience associated with treatment also affect patient perceptions and evaluations of satisfaction with the treatment. Finally, the individual's intentions, as manifested by their willingness to continue therapy, or his/her preference for, or choice of the treatment over other alternative treatments are relevant.
 | | |

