| 95% confidence interval half width | 2.152 | 2.345 | 1.669 | 1.819 | | | | | | | | | | | | | | | | | |
| Standard error (SE) | 1.098 | 1.196 | 0.852 | 0.928 | | | | | | | | | | | | | | | | | |

| | |
|------------------------------|---|
| 
Data analysis:
 | 
Descriptive analysis will be means, medians, quantiles, proportions (with their respective 95% confidence intervals and SE when relevant) and contingency tables according to the nature of the variables. As a dispersion measurement the standard deviation and the interquartile range will be calculated.
 
The statistical analysis will be done on all evaluable patients i.e. patients who enter the study without inclusion-exclusion criteria violations and with at least one TSQM-9 domain score (effectiveness, convenience and global satisfaction) calculated. Patients with missing values will not be excluded from the analysis, their data will not be replaced; frequency of missing data will be given for all analyzed variables. Lost to follow up patients will be analyzed until their last available visit.
 
The study objectives will be evaluated as described below.
 
Primary objective
 
The patients' satisfaction for medical treatment will be assessed by the 9-item Treatment Satisfaction Questionnaire for Medication (TSMQ-9) at each study visit (46). It is composed by 3 domains covering efficacy, convenience and global treatment satisfaction. TSQM-9 scores will be calculated according to author's instructions and summarized at each time point on all evaluable patients. Patients lost to follow up will be considered until their last available visit.
 
The patients switching treatment during observation period will not be excluded from analysis and will be evaluated at each visit as above described. Few patients are expected to stop treatment during study; if any, for primary objective evaluation they will be censored at the latest available visit. Comparisons of satisfaction between different treatment/devices are not matter of this study, throughout all analysis treatments will be lumped together.
 
Secondary objectives
 
#1 To describe patient disease perception (B-IPQ), adherence to COPD treatment (MMAS4), health status (CAT) and dyspnea (MMRC) during a 12-month observation period
 
A description of B-IPQ, MMAS-4, CAT and MMRC scores will be provided at baseline and at follow-up visits. Scale scores will be summarized at each time point. Patients lost to follow up will be considered until their last available visit. Missing items of questionnaires/scales will be replaced where applicable according to scoring algorithms.
 
#2 To analyse the relation between treatment satisfaction for medical treatment and demographic/clinical parameters and PROs during a 12-month observation period
 
Three regression models (one for each TSQM-9 domain score) will be estimated; the dependent variable will be domain score and the independent ones will be: age and gender (at enrollment), number of exacerbations, relevant spirometry parameters, level of dyspnea (MMRC score), impact of COPD on a patient's life (CAT) and treatment adherence (MMAS-4 score) collected during observational period. Because dependent variable will be collected at each study visit, repeated measures models will be estimated taking into account all available values for dependent and independent variables.
 
#3 To describe the health care resources utilization and related cost during a 12-month observation period
 
The health care resources consumption will take into consideration the following
 |

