8. RESEARCH QUESTION AND OBJECTIVES

Treatment satisfaction in COPD is associated with disease knowledge: subjects who claim to be more informed are more satisfied with their management. Long-term data on the patients' satisfaction to COPD medical treatments (i.e. pharmacological and not pharmacological treatment) in Italy are scarce. Further, there is limited information on the relation between satisfaction and clinical and patients' parameters. The present study will explore the patients' satisfaction to COPD medical treatment in a clinical real- world setting and how this is related to clinical parameters, quality of life, illness perception and treatment adherence evolution during 12-month follow up.

The patients will be also described as far as health status, presence of dyspnea, exacerbation occurrence, patient disease perception and awareness and adherence to COPD treatment during a 12-month follow up. Finally, health care resources utilization and related cost according to the Italian National Health Service during 12-month observation will be estimated and the correlation between patients' satisfaction and resource utilization will be assessed.

Primary Objective

To describe the patients' satisfaction to COPD medical treatments (by means of the TSQM9) during a 12-month observation period (namely, at enrolment, and after 6 and 12 months) in real- world setting.

Secondary Objectives

5. To describe patient disease perception (by means of illness perception questionnaire B-IPQ), adherence to COPD treatment (by means of MMAS4), health status (by means of CAT questionnaire) and dyspnea (by means of MMRC) during a 12-month observation period.
6. To analyze the relation between treatment satisfaction and demographic (such as age, gender), clinical (such as number of exacerbations, spirometric parameters) parameters and PROs during a 12-month observation period.
7. To describe the health care resources utilization and related cost according to the Italian National Health Service (INHS) during a 12-month observation period.
8. To assess the correlation between patients' satisfaction and resource utilization.

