9.13 LIMITATIONS OF THE RESEARCH METHODS

This is a non-interventional (observational) study which puts patients under observation for one year prospectively. However information, selection and/or recall bias have to be taken into account, as in all non-interventional studies.

Investigators could select patients in order to enroll those ones who most probably will be followed up or most probably correctly understand the questionnaires (selection bias). In order to limit this bias, monitoring visits could be randomly performed in sites to verify whether enrolment was performed consecutively.

The information to be captured is usually recorded in medical charts or on questionnaires filled in during visit: this also should limit recall bias of information.

As regards confounding, the primary aim of the study is to evaluate the patients' satisfaction for medical treatment irrespective of the ongoing treatment, no causality nor associations to treatments will be evaluated because of the lack of a control group. The regression models to analyze the relation between treatment satisfaction scores and demographic, clinical and PROs parameters during a 12-month observation (secondary objective #2) will provide adjusted estimates of the impact on satisfaction scores of each variable keeping constant the others included in the models.

Patients with missing values will not be excluded from the analysis, their data will not be replaced; frequency of missing data will be given for all analyzed variables. Patients with missing and not missing values in TSQM9 domain scores will be described according to main socio-demographic and clinical features.

As far as generalizability of results, the study aims to provide information on COPD patients enrolled in the study; it does not mean to be generalized to the population of Italian COPD patients, because sites are selected. However sampling is based on consecutive enrolment, in order to avoid patient selection during recruitment.

Finally, target sample size is considered to be achievable during the enrolment period on the basis of preliminary feasibility considerations.

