Table 17. Relation between treatment satisfaction and demographic/clinical parameters and PROs during 12 month observation period (Repeated measures regression models) – Effectiveness domain

A regression model will be estimated; the dependent variable will be the effectiveness domain score of TSQM-9 and the independent ones will be the following:

- age and gender at enrollment;
- number of exacerbations at enrollment;
- relevant spirometry parameters at enrollment (a selection of the following parameter will be done, based on data availability: FEV1, FVC, FEV1 % of the predicted, RV, TLC, DLCO);
- patient's disease severity in terms of level of dyspnea (mMRC score) or CAT total score (depending on data availability) at enrollment (since they are expected to be intercorrelated measures, as reported by 2017 GOLD guidelines, only one of such measures will be considered in the model);
- MMAS-4 score at enrollment.

Center will be included as random effect and study visit (visit1/enrollment, visit2/6months, and visit3/12months) as timepoint.

During data elaboration, the Biostatistician will assess the intercorrelation between the proposed variables, in order to evaluate the opportunity to exclude some of the listed independent variables that are highly associated to each other; in case of important lack of data for certain parameters, such parameters may be excluded as well from the final model.

Because measures referred to the dependent variable will be collected at each study visit, a mixed model for repeated measures will be estimated; moreover, interaction terms between independent variables will be evaluated and, if not significant, they will not be included in the final model. The optimal covariance structure will be evaluated during analysis (preferably "first-order autoregressive correlation" or "unstructured" options). A stepwise selection method will be evaluated during the analysis in order to identify the variables to be included in the final model.

The patients switching treatment during observation period will not be excluded from analysis. The patients stopping treatment during study will be censored at last available visit.

The analysis will be performed considering only evaluable patients at 12 months.

Table 18. Relation between treatment satisfaction and demographic/clinical parameters and PROs during 12 month observation period (Repeated measures regression models) – Convenience domain

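### Objective #2: the SAP's joint models give only the part of the spirometry and exacerbation relation not shared with symptoms and adherence; a minimally adjusted estimate should stand beside it

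*Protocol*

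**What the plan says.** Protocol section 8 states the objective as "To analyze the relation between treatment satisfaction and demographic (such as age, gender), clinical (such as number of exacerbations, spirometric parameters) parameters and PROs"; SAP section 1 repeats it. Protocol sections 4 and 9.7 plan one regression per TSQM-9 domain, with age, gender, exacerbations, spirometry, MMRC, CAT and adherence as joint covariates. The list closes with "and treatment adherence (MMAS-4 score) collected during observational period". Protocol 9.13 describes the output as "adjusted estimates of the impact on satisfaction scores of each variable keeping constant the others included in the models".

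SAP 4.9 keeps the joint repeated-measures model and changes its content:
- Covariates are enrolment values only, an explicit departure from protocol 9.7; only TSQM-9 varies by visit.
- One of mMRC or CAT enters, not both. "MMAS-4 score at enrollment" stays in the list.
- Spirometry parameters are chosen by data availability. Highly associated or poorly recorded covariates may be dropped, and stepwise selection may be used.
- The analysis is called exploratory, and a reason is given for including the PROs: satisfaction may depend on clinical status, as captured by mMRC or CAT, and on adherence.

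The protocol background states both directions. One sentence reads "Outcomes of treatment, including impact on symptoms and adherence with the treatment regimen, represent an important determinant of treatment satisfaction". Another reads "Patient satisfaction with their medication is shown to affect treatment-related behaviors", and goes on to list adherence among those behaviours.

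**The concern.** The objective names exacerbations and spirometry as things whose relation with satisfaction is wanted. By the plan's own account, symptoms are a route by which poor lung function and exacerbations would reach satisfaction. A coefficient that holds the symptom score constant leaves that route out. It answers a narrower question: what relation remains among patients with the same symptoms and adherence. If selection drops spirometry or exacerbations, the model reports nothing on them.

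MMAS-4 raises a second issue. The background lets adherence be a cause or a consequence of satisfaction, so a coefficient adjusted for it cannot be read as an impact. At stake is a report that finds no relation with lung function or prior exacerbations when the relation runs mainly through symptoms.

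**Working it through.** **The plan's own figure.** The only computed design figure is protocol Table 2 (precision of the mean global satisfaction score). With SE = SD/√N and half-width = 1.96 × SE, SD 21.4 gives 1.098 and 2.152 at N=380, and 1.196 and 2.345 at N=320. SD 16.6 gives 0.852 and 1.669, and 0.928 and 1.819. All reproduce. Nothing is computed for objective #2.

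**Inputs.** N = 320 to 380 is the protocol 9.5 evaluable range, taken as a stand-in for the 12-month set that SAP 4.9 uses. Two-sided 0.05 is assumed. Every correlation below is an assumption.

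**Step 1: effect of holding symptoms constant.** Let F be lung function, S symptoms and Y satisfaction, all standardised. The adjusted coefficient is (r_FY − r_FS·r_SY)/(1 − r_FS²). Power is by Fisher z. Take r_FS = −0.5 and r_SY = −0.4, so r_FS·r_SY = 0.20 and 1 − r_FS² = 0.75.

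| Share through symptoms | Unadjusted | Adjusted | Power unadjusted (N=320/380) | Power adjusted (N=320/380) |
|---|---|---|---|---|
| 100% | 0.200 | (0.200−0.20)/0.75 = 0 | 95%/98% | 5%/5% |
| 70% | 0.258 | (0.258−0.20)/0.75 = 0.077 | about 100% | 26%/30% |
| 50% | 0.320 | (0.320−0.20)/0.75 = 0.160 | about 100% | 77%/84% |

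The coefficient shrinks by the mediated share. On the protocol's SDs for global satisfaction (16.6 and 21.4), 0.32 is 5.3 to 6.8 points per SD of lung function, and 0.16 is 2.7 to 3.4 points.

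**Step 2: range.** Over |r_FS| 0.3 to 0.6 and |r_SY| 0.3 to 0.5, full mediation takes an unadjusted 0.09 to 0.30 to zero. Half mediation takes 0.165 to 0.441 down to 0.083 to 0.221. At the weak end (both 0.3, full mediation) the unadjusted 0.09 itself has only 36%/42% power.

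**Step 3: does the SAP's enrolment-only rule remove this?** A simulation (1,000 runs per setting) took lung function, exacerbations, symptoms and adherence at baseline and satisfaction as the mean of three visits, with no centre effect. Under full mediation:
- Lung function alone: 0.23, significant in 99%/100%. With symptoms, adherence and exacerbations in the model: 0.00, significant in 5%/6%.
- Exacerbations alone: −0.165, significant in 89%/94%. In the full model: 0.00, significant in 5%/4%.

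Part of that gap comes from lung function and exacerbations adjusting each other. With only those two in the model the coefficients are 0.19 and −0.11. The rest is symptoms and adherence. With half mediation, lung function in the full model is 0.20, significant in 96%/99%. So the enrolment-only rule does not remove the effect, and the coefficient does not generally vanish.

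**Step 4: MMAS-4 as a consequence of satisfaction.** If satisfaction drives adherence with standardised effect g, and a covariate acts on satisfaction with effect b and on adherence only through satisfaction, then adjusting for adherence shrinks b by g²(1−b²)/[g²(1−b²)+(1−g²)].
- g=0.2, b=0.5: 0.030/0.990 = 3%.
- g=0.5, b=0.3: 0.2275/0.9775 = 23%.

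This applies to same-visit satisfaction. At 6 and 12 months, enrolment MMAS-4 carries it only through the within-patient residual correlation ρ, so the three-visit average is multiplied by (1+2ρ)/3. For an assumed ρ of 0.3 to 0.7, the range becomes 3% × 0.53 = 2% to 23% × 0.80 = 19%. If covariates also affect adherence directly, the bias can go in either direction.

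**The case against.** The strongest reply is that this is a choice of estimand, openly made. Objective #2 names the PROs as targets alongside the clinical parameters, SAP 4.9 explains their inclusion and calls the work exploratory, and protocol 9.13 says that the estimates are mutually adjusted. That stands: the joint model is not an error.

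Other points also stand in part:
- A reader might infer from the protocol wording that symptoms and adherence measured during follow-up are adjusted for. SAP 4.9 supersedes that timing.
- A reader might infer that nothing unadjusted is planned. SAP Table 37 correlates 12-month TSQM-9 scores, without adjustment, with hospitalisations, ER accesses and the number of therapies for exacerbations and COPD-related adverse events. Because SAP section 3 defines moderate and severe exacerbations by treatment and admission, this comes close to exacerbation burden after enrolment. It is not the number of exacerbations, nor the enrolment count used in the models.
- Protocol 9.7 allows satisfaction to be looked at by lung-function group. This is optional, and SAP section 4 has no satisfaction table by severity class.
- The layouts of Tables 17-19 in SAP section 5 cannot be read, so an unadjusted column there cannot be excluded.
- Selection may remove the symptom or adherence term, which moves the clinical coefficients back towards their unadjusted values. It may equally remove the clinical variable.

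**Conclusion.** The point holds as a gap in reporting. The readable text of SAP 4.9 specifies only the joint model, and no readable table gives the unadjusted relation of TSQM-9 with spirometry or with number of exacerbations. The planned coefficients answer a narrower question than the objective asks. How much narrower depends on correlations that the documents do not give: half of the relation is lost if half runs through symptoms, and all of it only under full mediation.

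Two stronger readings are not supported. One is that the plan will hide a real relation with lung function. That needs full or near-full mediation, and with half mediation under the mid-range assumptions the adjusted coefficient is still found with 77% to 84% power. The other is that including MMAS-4 necessarily shrinks the other coefficients. The 3% to 23% figure is one special case.

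This is a cheap improvement to an exploratory secondary analysis. The primary objective is untouched.

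**What to change.** - In Tables 17-19, report for every pre-defined variable, whether or not it is retained in the final model, the coefficient and 95% CI from the same repeated-measures model with only that variable plus age, gender, visit and centre. Put it next to the full-model coefficient and use the same patients. Where a variable was dropped for missing data, state the number of patients behind its estimate.
- State in SAP 4.9 that the overall relation with spirometry and exacerbations is read from the first column, and that the full model gives the symptom- and adherence-adjusted association.
- Show the full model with and without MMAS-4.
- In protocol 9.13, replace the word impact with association.

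The cost is a few more runs of a model already planned and extra columns in three tables, with no new data. The drawback is more estimates to present in an exploratory analysis. The added column also cannot rescue weak relations: one of 0.09 would still be missed more often than found.

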5. AMENDMENTS AND UPDATES

Any change or addition to the protocol requires a written protocol amendment that must be approved by BITSPA and all main responsible parties, the principal investigator and the relevant EC before implementation. Amendments only affecting administrative aspects of the study do not require formal protocol amendments or EC approval but the ECs have to be informed of such administrative changes.

6. MILESTONES

The first patient enrolled in the study is expected in November 2015. The end of the data collection (including the follow-up period) is expected within July 2017, depending on the effective enrolment period necessary to collect data from about 400 consecutive COPD patients to be enrolled in approximately 8 months (from first patient enrolled).

| Milestone | Planned Date |
|--------------------------------|---------------------|
| Start of data collection | November 2015 |
| End of data collection | July 2017 |
| Final report of study results: | December 2017 |

7. RATIONALE AND BACKGROUND

COPD is a debilitating disease characterized by poorly reversible airflow limitation, breathlessness on exertion (1-2), exercise intolerance (3) and limitations in the capacity to perform daily activities (4-5).

In studies that have explored patient perspectives regarding the burden and impact of COPD, predominant complaints are shortness of breath and limitations in the ability to participate in activities (6), which negatively impact on social interactions and result in loss of independence (7-8).

Patient satisfaction with their medication is shown to affect treatment-related behaviors, such as their likelihood of continuing to use their medication, to use their medication correctly and to adhere with medication regimen (9). Treatment satisfaction may give useful insights not only into the patients' perspective on their current treatment but also about differentiation among alternative treatments. Treatment satisfaction is defined as the individual's rating of important attributes of the process and outcomes of his/her treatment experience (11). It focuses on one aspect of satisfaction with medical care and involves the interaction of expectations, preferences, and satisfaction with medical treatment. Treatment satisfaction assessment is potentially useful for understanding the patient's perspective on their current treatment and can be helpful to differentiate among alternative treatments (14-15). Patient expectations, demographic characteristics, such as age and education, and personal preferences affect treatment satisfaction. The pattern and characteristics (that is, side effects and effectiveness) of ongoing treatments for COPD, and the duration/severity of COPD influence perceptions of treatment satisfaction. More important are the factors most directly connected to the treatment, and the way the treatment is delivered and directly experienced by the patient. Outcomes of treatment, including impact on symptoms and adherence with the treatment regimen, represent an important determinant of treatment satisfaction. In 2012 only the 14.3% of Italian patients affected by obstructive respiratory syndromes was adherent to treatment (48).

The complexity, discomfort and convenience associated with treatment also affect patient perceptions and evaluations of satisfaction with the treatment. Finally, the individual's intentions, as manifested by their willingness to continue therapy, or his/her preference for, or choice of the treatment over other alternative treatments are relevant.

Satisfaction to treatment is related to adherence and willingness to continue treatment (16). Almost half of patients with COPD do not adhere to their medications (32). Illness and medication beliefs are important determinants of adherence in COPD. A recent study showed that in an a cohort of adults with COPD from New York and Chicago, concerns about medications (evaluated by means of Brief Illness Perception Questionnaire and the Beliefs about Medications Questionnaire) were associated with non-adherence evaluated by means of Medication Adherence Report Scale (32).

Although guidelines recommend monitoring symptoms in patients with COPD, there is limited information on the longitudinal changes in patient-reported dyspnea (PRD) related to activities of daily living. In a observational cohort study of symptomatic patients with stable COPD evaluated every 6 months for 2 years, PRD scores on the modified Medical Research Council (MMRC) scale demonstrate progression over two years despite stable lung function (36). Moreover, the course of COPD can be affected by acute events characterized by a worsening of the patient's respiratory symptoms that is beyond normal day-to-day variations and leads to a change in medications, known as exacerbations (33).

COPD exacerbations have serious negative impact on patient quality of life, lung function, and socioeconomic costs so their prevention, early detection, and prompt treatment have a great importance in the management of the disease. Despite treatment with maintenance medications, COPD patients continue to have exacerbations, so new medications and disease management interventions are warranted to reduce the severity and frequency of exacerbations and the related cost impact of the disease (34). The COPD assessment test (CAT) is a useful tool for the measurement of the health status during the exacerbation and for evaluation of recovery; in an observational, prospective study aimed at assessment of the course of CAT scores during bacterial exacerbations of COPD treated in outpatient setting, a significant improvement in the patient's health status during recovery from exacerbation as compared to their health status at the time of exacerbation was found (35).

Literature data in Italian real world setting about the relation between treatment satisfaction and clinical parameters and PRO are lacking. In a general population survey conducted in ten countries of the Middle East and North Africa region, together with Pakistan on COPD subjects with respiratory symptoms the treatment satisfaction was relatively high, with 83.2% of respondents somewhat or very satisfied with their physician's management. Treatment satisfaction was associated with not having exacerbations and with knowledge, subjects who claimed to be more informed being more satisfied with their management (37). Chronic obstructive pulmonary disease is a major cause of chronic morbidity and mortality worldwide, and its epidemiological, clinical, and socioeconomic impact is progressively increasing. A first estimate of the economic burden of COPD in Italy was conducted in 2008 (the SIRIO [Social Impact of Respiratory Integrated Outcomes] study) (40). Average direct costs and total societal costs in the year before enrollment were €2,932 and €3,291, respectively. Direct cost was €2,461 (hospitalization: €1,570; outpatient: €344; and pharmaceutical: €547) in the first year of follow-up, while total societal cost was €2,707. The therapeutic approach followed in a specialist center, based on the application of clinical guidelines, has been shown to be a highly effective investment for the long-term management of COPD. A small increase of pharmaceutical costs per year allowed a substantial saving in terms of hospitalizations, costs related to outpatient services, and indirect costs.

Patients with COPD are at increased risk for lung infections and other pathologies (eg, pneumonia). A study on two cohorts of 84130 COPD patients each, showed that COPD patients with newly developed pneumonia have higher health care resource utilization and/or costs in all areas explored: hospitalizations, outpatient visits, ER visits, and prescription costs (38). In this study, the pneumonia cohort was approximately nine times more likely to have a hospitalization and four times more likely to have an ER visit during the 12 months of follow-up. A total cost savings of \$22348 was estimated to be associated with the prevention of pneumonia based on the sum of the mean differences of \$14353 in inpatient costs, \$6891 in outpatient costs, and \$1104 in pharmacy costs between the pneumonia and control cohorts.

Poor adherence to treatment may contribute to the treatment gap in COPD. A large population-based study have shown that reduced adherence to treatment with tiotropium (TIO) alone or co-administered with fluticasone propionate/salmeterol (TIO + FSC) is associated with increased risk for exacerbations and higher health care utilization in COPD patients (39).

